5.3. Subject Discontinuation and Withdrawal

The subject is free to permanently discontinue study medication at any time, without prejudice to further treatment. Discontinuation from study medication is not the same as complete withdrawal from the study (i.e., withdrawal of consent).

Protocol FGCL-4592-096 A01

Subjects may withdraw consent and discontinue from the study at any time by discontinuing study medication and refusing to return for any form of follow-up without any prejudice.

A subject who decides to discontinue study medication will always be asked about the reason(s) to discontinue study medication and the presence of AEs (if any). These data will be ascertained and documented by the investigator and recorded in the eCRF as appropriate. Any subject discontinuing study medication will be followed up for 28 days after discontinuing study medication whenever feasible for purposes of adverse event reporting.

Reasons for permanent discontinuation of study medication:

- Subject's decision (subject no longer wants to continue study medication (i.e., withdrawal of consent)
- Investigator's decision that it is in the best interest of the subject to be withdrawn from the study
- Adverse events
- Significant noncompliance with study procedures, as determined by Investigator or Sponsor
- Lack of efficacy / Meets ESA withdrawal criteria
- Subject is lost to follow-up
- Subject got transferred to a different location/dialysis center
- Subject is no longer requiring dialysis due to kidney transplant
- Site terminated by the sponsor
- Pregnancy
- Death

Upon discontinuation from the study, both female subjects of childbearing potential and male subjects with partners of childbearing potential must continue to use a medically acceptable method of contraception for 1 week following the last study drug administration.

5.4. Replacement of Subjects

Subjects will not be replaced from this study.

6. INVESTIGATIONAL PRODUCT

6.1. Formulation

Roxadustat is supplied by FibroGen, Inc. as red coated, tablets for oral administration, in strengths of 20 mg, 50 mg, 70 mg, 100 mg and 150 mg. The excipients include lactose monohydrate, microcrystalline cellulose, povidone, croscarmellose sodium, magnesium stearate, and colorant Red Opadry II. All ingredients used for manufacture of roxadustat comply with US and European Union compendia or regulatory standards. Strengths are different in size and debossing reflects the strength (i.e., 20, 50, 70, 100 or 150 mg). Due to the light-sensitive nature of roxadustat and to minimize exposure of the active pharmaceutical ingredient to light, tablets should remain in the original packaging for as long as possible and be administered as intact tablets only.

6.2. Storage

Roxadustat tablets should be protected from light, and stored at room temperature between 15°C and 30°C (59°F to 86°F).

Study drug should be stored in a securely locked area to which access is limited to appropriately authorized study personnel.

6.3. Study Drug Handling and Disposal

Study drug and packaging provided by the Sponsor should be retained at the site until otherwise instructed in writing by the Sponsor. Upon completion of the study or termination of the investigational site, all used, unused, and partially used study drugs; and all study drugs that were not dispensed will be shipped to a site designated by the Sponsor or may be destroyed according to local/institutional policies by the Pharmacy/authorized staff after drug accountability and reconciliation has been completed by Sponsor.

6.4. Route of Administration and Dose

Route of Administration: Oral (all tablets must be administered whole)

Dosing Frequency: Subjects will be dosed three times weekly (TIW), except if a subject requires < 60 mg/week to maintain Hb levels, in which case dose frequency may be reduced in a stepwise fashion, e.g., to twice weekly (BIW), then once weekly (QW), then every-2-weekly (Q2W), etc. The first dose of roxadustat should be administered on Day 1 after completion of all procedures including laboratory draws. Roxadustat doses should be administered at least 2 days apart, and no more than 4 days apart. Dosing should occur at approximately at the same time of day. Roxadustat can be taken with or without food. If phosphate binders are taken with food, roxadustat is advised to be taken at least one hour before or one hour after the phosphate binder.

6.5. Overdose, Emergency Procedures and Management of Overdose

The maximum allowed roxadustat dose is 400 mg or 3.0 mg/kg/dose, whichever is lower. Any dosing exceeding the maximum allowed roxadustat dose should be reported within 24 hours. The Medical Monitor should be contacted as soon as possible. Symptoms associated with overdosing, if any, will be reported as adverse events.

Protocol FGCL-4592-096 A01

In the event of suspected roxadustat overdose, the subject should receive supportive care and monitoring. The Sponsor's Medical Monitor should be contacted as applicable.

7. STUDY PROCEDURES

7.1. Study Procedures by Visit/ Schedule of Assessments

During study visits, unless otherwise indicated, it is preferred that all assessments including labs and physical examinations should be completed prior to dialysis.

Table 4: Schedule of Assessments

Visit / Week:	Screening Visit	Day 1	Wk 2 to 8 (Every 2 weeks ± 4 days)	Wk 12 to 24 g (Every 4 weeks ± 4 days)	Post-Treatment ° or ET ± 7 days
Written informed consent	X				
Eligibility criteria	X	X			
Demographics and medical history	X				
Height, weight	X	X a			
Blood pressure, heart rate, temperature	X	X	X	X	X
Physical Exam	X			Χ°	
Hemoglobin (central and local)	X d		X f	X f	X d
CBC with WBC differential	X	X	Wks 4, 8	Wks 16, 24	X
Serum chemistry	X	X	Wks 4, 8	Wks 16, 24	X
СРК	X	X	Wk 8	Wks 16, 24	
Serum iron, ferritin, TIBC, TSAT, CHr, reticulocytes	X	X	Wk 8	Wks 16, 24	
HIV ELISA, HBsAg, anti-HCV Ab	X				
Serum hCG pregnancy test	X b			Q8Wks	X
Dose adjustment			X	X	
AE/CM recording	X	X	X	X	X
Study drug dispensing		X	X	X	

Ab = antibody; CBC = complete blood count; CHr = reticulocyte hemoglobin content; ELISA = enzyme-linked immunosorbent assay; ET = early termination; HBsAg = hepatitis B surface antigen; hCG = human chorionic gonadotropin; HCV = hepatitis C virus; HIV = human immunodeficiency virus; LFTs = liver function tests; TIBC = total iron binding capacity; TSAT = transferrin saturation; WBC = white blood cells; Wk(s) = week(s)

- Collect from female subjects of child bearing potential only b
- Physical Exam to be performed during W24/End of Treatment (EOT) visit only
- Central labs only 28 days post last dose of roxadustat
- Collect a separate central Hb only when CBC is not collected Week 24 = EOT

Page 43 of 69

7.2. Screening Period

- Signed written informed consent
- Inclusion/Exclusion criteria verification
- Demographics and medical history
- Height and weight
- Vital signs (BP, HR, temperature)
- Physical Examination: HEENT, respiratory, cardiovascular, abdomen, extremities, and neurological parameters
- Laboratory tests:
 - o Hemoglobin (central)
 - o Complete blood count (CBC) with WBC differential
 - o Serum chemistry
 - o CPK
 - Serum iron, ferritin, total iron-binding capacity (TIBC), transferrin saturation (TSAT),
 Reticulocyte count and hemoglobin in reticulocytes (CHr)
 - o Enzyme-linked immunosorbent assay (ELISA) for HIV
 - o Hepatitis B surface antigen (HBsAg)
 - o Anti-HCV Ab
 - o Serum hCG pregnancy test
- Renal ultrasound or other imaging may be performed during screening to rule out renal cell carcinoma or suspicion of renal cell carcinoma if deemed necessary by the PI.
- Review and record concomitant medications
- Review and record procedures and nondrug therapies
- Review and record AEs, if any (capture the event under medical history, if applicable)

7.2.1. Additional Screening Assessments

If a subject's laboratory results do not meet eligibility criteria at Screening, specific laboratory assessments may be repeated within the Screening Period.

If a subject fails screening, he/she may be re-screened (as a new patient) once deemed appropriate by the investigator. Where possible, an approval should be obtained from the Medical Monitor prior to re-screening.

7.3. Treatment Period

The Treatment Period begins on the first day of dosing with study treatment (Day 1).

7.3.1. Day 1

All assessments are to be completed prior to first dose of study drug

- Inclusion/Exclusion criteria verification
- Weight
- Vital signs (BP, HR, temperature)
- Estimated dry weight
- Local Hb assessment
- Laboratory tests:
 - o Complete blood count (CBC) with WBC differential

Protocol FGCL-4592-096 A01

- o Serum chemistry
- o CPK
- Serum iron, ferritin, total iron-binding capacity (TIBC), transferrin saturation (TSAT),
 Reticulocyte count and hemoglobin in reticulocytes (CHr)
- Hemoglobin local
- o AE/CM recording
- o Study drug administration

7.3.2. Weeks 2 to 8 (Every 2 Weeks, ± 4 days)

- Vital signs (BP, HR, temperature)
- Laboratory tests:
 - o Hemoglobin (central and local lab)
 - Draw a central Hb only on visits CBC is not collected
- Week 4 and Week 8:
 - o Complete blood count (CBC) with WBC differential
 - o Serum chemistry
- Week 8:
 - o CPK
 - Serum iron, ferritin, total iron-binding capacity (TIBC), transferrin saturation (TSAT),
 Reticulocyte count and hemoglobin in reticulocytes (CHr)
- Dose review at every visit and dose adjustment every 4 weeks
- TEAE/CM recording
- Study drug dispensing

7.3.3. Weeks 12 to 24 (Every 4 weeks, ± 4 days)

- Vital signs (BP, HR, temperature)
- Physical Examination: HEENT, respiratory, cardiovascular, abdomen, extremities, and neurological parameters (at Week 24/EOT only)
- Hemoglobin (central as part of CBC and local lab)
- Week 16 and Week 24:
 - o Complete blood count (CBC) with WBC differential
 - o Serum chemistry
 - o CPK
 - Serum iron, ferritin, total iron-binding capacity (TIBC), transferrin saturation (TSAT),
 Reticulocyte count and hemoglobin in reticulocytes (CHr)
- Every 8 Weeks:
 - o Serum hCG pregnancy test (female of child bearing potential only)
- Dose adjustment
- AE/CM recording
- Study drug dispensing

Week 24 visit is considered as End of Treatment (EOT) visit

Roxadustat Protocol FGCL-4592-096 A01

7.4. Post-Treatment (subjects discontinuing roxadustat treatment) or Early Termination (ET) (±7 days)

Subjects permanently discontinuing roxadustat should have one final safety assessment 28 days after the last roxadustat dose.

- Vital signs (BP, HR, temperature)
- Laboratory tests:
 - o Complete blood count (CBC) with WBC differential
 - o Serum chemistry
 - o Serum hCG pregnancy test (female of child bearing potential only)
 - o AE/CM recording

Subjects who wish to permanently discontinue roxadustat, should receive the first ESA dose at least two days after the last roxadustat dose.

An extension of roxadustat treatment after 24 weeks may be offered to interested subjects within the context of this study protocol upon agreement of the study site until roxadustat is commercially available, or up to 1 year after completing the 24 weeks, whichever comes first.

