4. STUDY DESIGN

4.1. Description of the Study

[figure not shown]
This open-label single arm study is designed to evaluate roxadustat in maintaining Hb in ESRD subjects receiving in-center HD either after conversion from a stable ESA dose: ESA use ≥ 6 weeks prior to conversion to roxadustat dosing or as initial anemia treatment, in subjects with < 6 weeks of total ESA use prior to start of roxadustat dosing.

The study periods are:

- o Screening Period: Up to 6 weeks
- o Treatment Period: 24 weeks
- Post-Treatment Follow-Up Period: Subjects permanently discontinuing roxadustat, should have one final safety assessment (TEAEs and TESAEs) 28 days after the last roxadustat dose.

An extension of roxadustat treatment after 24 weeks may be offered to interested subjects within the context of this study protocol upon agreement of the study site until roxadustat is commercially available, or up to 1 year after completing the 24 weeks, whichever comes first.

Figure 2: Study Design Overview

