4.3. Screening Period

After signing the informed consent, subjects enter the Screening Period. All screening procedures are to be completed within 6 weeks. Subjects will be evaluated per the protocol inclusion/exclusion criteria to determine eligibility for participation in this trial.

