4.7.5. Contraception

Female subjects of childbearing potential, if not practicing complete sexual abstinence, must agree to practice a dual method of contraception, for example, a combination of the following: (1) oral contraceptive, depo progesterone, or intrauterine device; and (2) a barrier method (condom or diaphragm). Male subjects (nonsurgically sterile; i.e., no vasectomy) with female partners of childbearing potential who are not on birth control must agree to use a barrier method of contraception (e.g., condom) or the female partner must agree to use contraception as described above unless practicing complete sexual abstinence.

Subjects must agree to practice above contraceptive methods, as applicable, for the entire duration of the study, from enrollment through the EOS visit. It is highly recommended that they continue to practice the contraceptive methods for 1 week following the last dose of study treatment. For subjects discontinuing study medication prematurely, it is recommended that they continue to practice contraceptive methods for 1 week following the last dose of study treatment.

Pregnancy, spontaneous or therapeutic abortion, or events related to pregnancy are to be reported on the study pregnancy form provided.

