5. STUDY ENROLLMENT AND WITHDRAWAL

5.1. Inclusion Criteria

A subject is eligible for the study if all of the following criteria are met:

- 1. Subject has been informed of the investigational nature of this study and has given written informed consent in accordance with institutional, local, and national guidelines
- 2. Subject is ≥ 18 years of age
- 3. Receiving in-center hemodialysis for end stage renal disease (ESRD)
- 4. Prior ESA use:
 - For a subject converting from an ESA: On ESA ≥6 weeks and the prescribed ESA dose remain stable (as determined by PI) during the 4 weeks prior to initiating roxadustat treatment
 - Subject is initiating anemia treatment: Defined as: < 6 weeks of prior ESA use or no prior ESA use.
- 5. Vascular access must be a functioning native arteriovenous fistula or graft with adequate flow in the opinion of the investigator, or permanent tunneled catheter.
- 6. Screening Hb (based on central lab value; measured within 10 days prior to initiating roxadustat treatment):
 - Subjects converting from an ESA: screening Hb is between 9.0 to 12.0 g/dL
 - Subjects initiating anemia treatment: screening Hb is < 10.0 g/dL
- 7. Ferritin ≥ 50 ng/mL, Transferrin saturation (TSAT) ≥ 10% at screening (subject may qualify after receiving iron supplement per local standard of care)
- 8. Subject's alanine aminotransferase (ALT) and aspartate aminotransferase (AST) are ≤ 3 x upper limit of normal (ULN), and total bilirubin (TBL) is ≤ 1.5 x ULN at screening and prior to initiating roxadustat treatment. TBL up to 2 x ULN may be allowed if AST and ALT are within normal limit)
- 9. Subject's body weight (estimated dry weight in HD subjects) is 45.0 to 160.0 kg

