- 17. Subject has any of the following known untreated conditions as determined by the investigator: proliferative diabetic retinopathy, diabetic macular edema, macular degeneration or retinal vein occlusion (subjects who are already blind may qualify to participate)
- 18. Subjects with prior organ transplant who have one of the following conditions or states
 - a) Experienced rejection of transplanted organ within 6 months of transplantation
 - b) Currently on high doses of immunosuppressive therapy (per discretion of the investigator)
 - c) Are scheduled for organ transplantation (on the waiting list for kidney transplant is not exclusionary)
- 19. Subject has participated in an interventional clinical study or has been treated with an investigational drug within 4 weeks prior to screening
- 20. Subject has drug-treated gastroparesis, short-bowel syndrome, or any other gastrointestinal condition that may lead to reduced absorption of study drug (determined by the investigator)
- 21. Subject has an anticipated use of dapsone or androgen in any dose amount or anticipated chronic use of acetaminophen or paracetamol > 2.0 g/day during the study
- 22. Subject has a history of alcohol or drug abuse within 6 months prior to screening as determined by the clinical judgment of the investigator
- 23. Females of childbearing potential, if not practicing complete sexual abstinence or using contraception as detailed in the protocol; male subjects (if not surgically sterile; i.e., no vasectomy) with sexual partners of childbearing potential, if not practicing complete sexual abstinence or using contraception
- 24. Pregnant or breastfeeding females
- 25. Subject has any medical condition that in the opinion of the Investigator may pose a safety risk to the subject in this study, which may confound efficacy or safety assessment, or may interfere with study participation

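### No pregnancy test is scheduled on Day 1 or at Weeks 2 to 8, so the first routine on-treatment test comes only after 12 or 16 weeks of dosing

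*Protocol*

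**What the plan says.** Protocol section 5.2 excludes "Pregnant or breastfeeding females" (criterion 24). Criterion 23 excludes "Females of childbearing potential, if not practicing complete sexual abstinence or using contraception as detailed in the protocol". Eligibility is checked at screening and again on Day 1, before the first dose (Table 4, section 7.3.1).

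The row "Serum hCG pregnancy test" in Table 4 is marked at Screening, blank for Day 1 and for Weeks 2 to 8, eight-weekly under Weeks 12 to 24, and marked again at Post-Treatment/ET. The visit lists agree. Section 7.2 includes the test, sections 7.3.1 and 7.3.2 do not, section 7.3.3 gives "Serum hCG pregnancy test (female of child bearing potential only" at the eight-weekly frequency, and section 7.4 includes it. SAP Appendix 1 repeats the pattern.

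On the age of screening results, section 4.1 states "Screening Period: Up to 6 weeks" and section 4.3 adds "All screening procedures are to be completed within 6 weeks". One screening laboratory value has a tighter limit: "Screening Hb (based on central lab value; measured within 10 days prior to initiating roxadustat treatment" (section 5.1, criterion 6). No such limit is written for hCG.

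**The concern.** Section 8.3.6 requires a pregnancy to be confirmed by serum hCG and a pregnant subject to be taken off treatment at once. The protocol thus intends to limit fetal exposure, and that depends on detecting the pregnancy. For the first 12 or 16 weeks on drug no scheduled test would detect one. A pregnancy present but undetected at first dose, or beginning soon after, would be found only if someone suspected it or the subject stopped early.

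There are two further gaps. The eight-weekly instruction can be read in two ways, so sites may test in different weeks. Also, the hCG supporting the Day 1 check of criterion 24 has no written age limit of its own. What is at stake is patient safety, not any efficacy estimate.

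**Working it through.** There is no plan figure to reproduce. The check reads the schedule and adds up days.

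**Inputs**
- Visits in the late block: Weeks 12, 16, 20 and 24, each ±4 days (Table 4, section 7.3.3).
- Dosing: three times weekly (section 4.5.2).
- Screening: up to 6 weeks = 42 days (sections 4.1, 4.3). I assume this is the longest time from a screening test to first dose.
- Qualifying Hb: within 10 days before first dose (section 5.1).

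**Which week is the first on-treatment test?** Counting in eights from the start of the block gives Weeks 12 and 20. Counting from Day 1 and keeping only visits in the block gives Weeks 16 and 24. Counting from Day 1 would also reach Week 8, but that cell of Table 4 is blank and section 7.3.2 lists no hCG. Either way there are two on-treatment tests.

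**Time on drug before that test**
- Week 12: 7 × 12 = 84 days (80 to 88 with the window); 12 × 3 = 36 scheduled doses.
- Week 16: 7 × 16 = 112 days (108 to 116); 16 × 3 = 48 scheduled doses.
- The window of 4 days is 4/7 × 3 = 1.7 doses either way.

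**Longest interval from screening hCG to first on-treatment hCG** = age of the screening hCG at first dose + days on drug.

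| Screening hCG | First test Week 12 | First test Week 16 |
|---|---|---|
| Same draw as qualifying Hb (at most 10 days old) | 10 + 84 = 94 days = 13.4 weeks | 10 + 112 = 122 days = 17.4 weeks |
| Separate from qualifying Hb (at most 42 days old) | 42 + 84 = 126 days = 18.0 weeks | 42 + 112 = 154 days = 22.0 weeks |

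A visit at the late edge of its window adds 4 days to each entry. Days before first dose carry no drug exposure.

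**When does each row apply?** Section 7.2 lists central Hb and hCG together, under a single Screening column in Table 4. One draw within 10 days of dosing satisfies the Hb rule and makes the hCG equally recent. The second row arises if screening is split over several draws, or if Hb alone is repeated, which section 7.2.1 allows. A formal re-screen is as a new patient, which implies a new hCG.

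**With the fix**
- Interval: 10 + 56 = 66 days = 9.4 weeks; with the window, 70 days = 10.0 weeks.
- On drug: 8 weeks, 8 × 3 = 24 scheduled doses, which is 36 − 24 = 12 or 48 − 24 = 24 fewer.
- On-treatment tests: three (Weeks 8, 16, 24) instead of two.

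**The case against.** The strongest reply is that this is a preference. No passage sets a testing frequency that the schedule fails to meet. The documents give no reproductive-toxicity data and refer detailed safety information to the Investigator's Brochure. The number of women of childbearing potential is not stated. This stands: a reader might infer an internal contradiction or a known number of exposed pregnancies, and the documents support neither. The 36 or 48 doses are scheduled doses. Holds and reduced frequency could lower them, and they describe exposure only for a pregnancy present at first dose and unsuspected throughout.

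A second reply is that screening results are normally more recent than 6 weeks. This also stands. A reader might take 18 or 22 weeks as the usual interval, but with one screening draw it is at most 13.4 or 17.4 weeks. Nor is the 10-day Hb limit a benchmark for pregnancy testing. HIV and hepatitis serology are also tested only at screening and carried to Day 1.

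A third reply is that safeguards exist. Contraception or abstinence is a condition of entry. Section 4.7.5 says "Female subjects of childbearing potential, if not practicing complete sexual abstinence, must agree to practice a dual method of contraception". Visits are every two weeks to Week 8 with adverse-event queries (sections 7.3.2, 8.3.2), unscheduled tests are allowed (7.6), drug may be interrupted on suspicion (8.3.6), and hCG is done at early termination. These lower the risk. But they prevent pregnancy, or act on suspicion, discretion or stopping. None routinely detects an unsuspected pregnancy during the first 12 or 16 weeks, so the gap remains.

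**Conclusion.** The point holds as a low-cost safety improvement. No hCG is scheduled at five consecutive visits (Day 1, Weeks 2, 4, 6 and 8), or six if the first on-treatment test is at Week 16. Women of childbearing potential therefore have 12 or 16 weeks on drug before a routine test. The interval between tests is at most 13.4 or 17.4 weeks when hCG and qualifying Hb share a draw, and at most 18 or 22 weeks when they do not. These are nominal maxima before the 4-day visit window, and the longer pair assumes the full 6-week screening period is used.

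The expected number of exposed pregnancies cannot be estimated from the documents. The efficacy endpoints, their analysis and the sample size are unaffected.

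**What to change.** 1. Add serum hCG for women of childbearing potential to the Week 8 visit, where serum is already drawn for chemistry and iron indices. State the on-treatment tests as Weeks 8, 16 and 24 in Table 4, sections 7.3.2 and 7.3.3, and SAP Appendix 1. This closes the early gap and removes the ambiguity.
2. In Table 4 and section 7.2, require a negative serum hCG within 10 days before first dose. Repeat it with the qualifying Hb draw only when the screening hCG is older than that. The 10 days reuses an existing limit and is not a pregnancy-specific threshold. A Day 1 draw would be weaker: hCG is a central-laboratory test (Table 5), and section 6.4 has the first dose follow the Day 1 draws, not their results. A pregnancy too early to detect before dosing would meet the Week 8 test.

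The cost is one extra on-treatment assay per woman of childbearing potential (three instead of two) and, for some, one repeat pre-dose assay. That repeat may need an added serum tube, since a repeat of Hb alone does not guarantee serum, but no added visit. The change needs a minor protocol amendment, with written IRB approval before implementation (section 12.2), and a matching SAP edit.
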